15. ETHICS

15.1. INDEPENDENT ETHICS COMMITTEE (IEC) / INSTITUTIONAL REVIEW BOARD (IRB)

This study can only be undertaken after full approval of the clinical study protocol, ICF, any other written information given to subjects, and subject recruitment materials has been obtained from the IEC/IRB. This approval document must be dated and clearly identify the study and the related study documents being approved, including the subject compensation programs.

During the course of study the following documents will be sent to the IEC/IRB for review:

- Changes to the Investigator's Brochure
- Reports of adverse events that are serious, unlisted and associated with the investigational drug

Substantial amendments and applicable ICF revisions must promptly be submitted to the IEC/IRB for review and approval prior to implementation of the change(s), except when necessary to eliminate an immediate hazard to the study subjects.

The IEC/IRB is responsible for continuous review of the study. At least once a year, the investigator will provide the IEC/IRB with a progress report to allow review of the study. Additional progress reports must be provided if required by the IEC/IRB. These requests and (re) approvals, if applicable, must be documented in writing.

15.2. REGULATORY APPROVAL / NOTIFICATION

This clinical study protocol, title and a list of clinical study centers, IEC(s)/IRB(s) approvals, as well as other relevant documentation will be submitted to the local Regulatory Authorities for review and approval prior to trial start. Upon completion, the Regulatory Authorities will be notified the study has ended. The study will only be undertaken in compliance with the local regulatory requirements.

15.3. ICH GOOD CLINICAL PRACTICE

This study will be conducted in accordance with the current ICH-GCP Guideline E6. Good Clinical Practice is an international ethical and scientific quality standard for designing, conducting, recording and reporting studies that involve the participation of human subjects. Compliance with this standard provides public assurance that the rights, safety and well-being of study subjects are protected, consistent with the principles that have their origin in the Declaration of Helsinki, and that the clinical study data are credible.

This study will be conducted in compliance with the Declaration of Helsinki (1964 and successive amendments), current GCP and the applicable European and local regulatory requirements.

15.4. INFORMED CONSENT

The investigator or designated personnel must explain the study and the implications of participation (e.g. objectives, methods, anticipated benefits and possible risks) to potential subjects or their legally acceptable representatives prior to any trial related activity. Subjects will be informed that their participation is voluntary and that they may withdraw from the study at any time. They will be informed that choosing not to participate or to withdraw from the study will not have an impact on the care the subject will receive for the treatment of his/her disease. In case the subject is unable to read and write, an impartial witness must confirm the informed consent.

The subject will be given sufficient time to read the ICF and to ask additional questions. After this explanation and before entry in the study, consent must be appropriately recorded by means of the subject's personally dated signature or by the signature of an independent witness who certifies the subject's consent in writing. After having obtained the consent, a copy of the signed and dated ICF must be given to the subject.

If new information becomes available that may be relevant to the subject's willingness to participate in the study, the subject will be informed in a timely manner by means of an updated ICF. This amended ICF will be signed and dated by the subject and the investigator to document the willingness of the subject to continue with the study.

This signed and dated amended version will be filed together with the initial signed and dated ICF.

16. FINANCING AND INSURANCE

16.1. FINANCIAL DISCLOSURE

The disclosed financial interest of the investigator must be collected before screening of the first subject, following study completion at the clinical study center and one year following overall study completion. The investigator must promptly update this information if any relevant changes occur during this period. Disclosable financial interests will be recorded on the Investigator Financial Disclosure Form.

Any investigator(s) added as investigational staff must complete the Investigator Financial Disclosure Form at the beginning of their participation in the study. For any investigator(s) leaving the clinical study center prior to study completion, an Investigator Financial Disclosure Form must be obtained at the end of their contribution to the study.

16.2. INDEMNIFICATION

The sponsor will indemnify the investigator and hold harmless the investigator and his or her medical staff from any claim for damages, demand or cost arising from the activities to be carried out in compliance with the clinical study protocol.

The investigator must notify the sponsor immediately upon notice of any claims or lawsuits.

16.3. INSURANCE

The sponsor ensures that suitable clinical study insurance coverage is in place prior to the start of clinical study. For subjects treated according to the clinical study protocol, injury possibly arising from participating in this study is covered by the liability insurance of the sponsor, unless malpractice from the investigator.

17. DATA QUALITY CONTROL / ASSURANCE

17.1. MONITORING

This clinical study will be monitored by sponsor representatives according to the current Standard Operating Procedure for the monitoring of clinical studies.

The monitor will perform on-site monitoring visits as frequently as necessary which will be documented on the monitoring log. Shortly before the study starts, the monitor will meet with the investigator and study staff involved to review the study-specific procedures on study conduct and recording the data in the eCRF. The first monitoring visit will take place as soon as possible after enrollment and the investigator shall permit the monitor to verify the progress of the study on a continues basis. The investigator shall make the eCRFs available, provide missing or corrected data and sign the eCRFs. Key data transcribed onto the eCRFs, such as the subject's sex, age, assessment dates, test results etc., will be reviewed against the available source documents. Personal information will be treated as strictly confidential and will not be made publicly available. Any inconsistency between source data and data recorded in the eCRF will be corrected.

The sponsor will ensure that appropriate QC steps are included into the different clinical study processes to guarantee adequate protection of the subjects and to guarantee the quality of the data.

1. STUDY DESIGN

1.1. STUDY OBJECTIVES

1.1.1. Primary Objective

- To evaluate the safety and tolerability of 4 different doses of GLPG2222 administered orally and q.d. for 29 days in adult subjects with CF* who are homozygous for the F508del CFTR mutation.

* Cystic Fibrosis

1.1.2. Secondary Objectives

- To assess changes in biomarkers of CFTR activity.
- To assess changes in respiratory symptoms.
- To assess the PK of GLPG2222.

1.2. STUDY ENDPOINTS

1.2.1. Primary Endpoint

- Safety and tolerability, assessed by the incidence of adverse events (AEs), as well as changes over time in weight, vital signs, oxygen saturation by pulse oximetry, 12-lead ECG, spirometry, and clinical safety laboratory data (hematology, chemistry, coagulation and urinalysis).

1.2.2. Secondary Endpoints

- Change from baseline in sweat chloride concentration through 29 days.
- Change from baseline in percent predicted FEV₁ through 29 days.
- Change from baseline in the respiratory domain of the Cystic Fibrosis Questionnaire-Revised (CFQ-R) through 29 days.
- PK parameters of GLPG2222.

1.3. STUDY DESIGN

This is a Phase IIa, multi-center, randomized, double-blind, placebo-controlled, parallel-group study to evaluate 4 different doses of GLPG2222 administered orally and q.d. for 29 days to adult male and female subjects with a confirmed diagnosis of CF and homozygous for the F508del CFTR mutation. Eligible subjects must be on a stable concomitant medication regimen for at least 4 weeks prior to the first study drug administration and agree to continue the same regimen for the duration of the study.

A schedule of the study design is provided in Figure 1.

[figure not shown]

Figure 1: Study design

The study will consist of a screening period of maximum 4 weeks (starting when the subject has signed the informed consent form [ICF]), a treatment period of 4 weeks, and a follow-up period of 2 weeks. Enrolled subjects will come to the clinical study center at screening, on Day 1 (baseline), Day 15, Day 29, and at the follow-up visit (2 weeks after the last study drug administration).

Approximately 50 evaluable subjects are planned to be included sequentially in the study: the first 25 subjects will be assigned to Cohort A (i.e. subjects 1 to 25) and the next 25 subjects will be assigned to Cohort B (i.e. subjects 26 to 50). Subjects participating in Cohort A are not allowed to participate in Cohort B. In each study cohort, subjects will be randomized in a 2:2:1 ratio to receive:

- Cohort A: 50 mg GLPG2222, 100 mg GLPG2222 or placebo q.d. for 29 days.
- Cohort B: 200 mg GLPG2222, 400 mg GLPG2222 or placebo q.d. for 29 days.

Assessments for efficacy and safety will be performed during the study at the time points specified in the flow chart.

Additionally, subjects can choose to participate in the optional substudy, in which nasal brushings will be collected.

Subjects will be in the study for a duration of minimum 6 weeks and maximum 10 weeks (from screening until the follow-up visit, depending on the duration of the screening period).

The end of the study is defined as the last contact with the last subject.

1.4. PROTOCOL AND PROTOCOL AMENDMENTS

Protocol Versions	Date (ddMMMyyyy)
Final	06DEC2016

Protocol Amendments	Date (ddMMMyyyy)
Not Applicable	

This SAP was based on the latest version of the protocol.

1.5. FLOWCHART

The schedule of assessments is given in the flow chart below.

EVENT	SCREENING	TREATMENT PERIOD ¹				FOLLOW-UP
		D1	D15 (±2D)	D29 (±2D)	ED	
Study days (D)	D-28 till D-1					
Informed consent ²	X					
Inclusion/exclusion criteria	X	X				
CFQ-R ³	X	X	X	X	X	X
Demographics	X					
Medical history	X					
Physical examination ⁴	X	X	X	X	X	X
Weight	X	X	X	X	X	X
Vital signs ⁵	X	X	X	X	X	X
Pulse oximetry ⁶	X	X	X	X	X	X
12-lead ECG ⁷	X	X	X	X	X	X

¹ All assessments are to be performed pre-dose. In addition, some assessments are also to be performed at defined time points post-dose when specifically mentioned.

² Written informed consent to be obtained before any study-related procedures and/or assessments are performed.

³ CFQ-R to be completed prior to any other assessments scheduled for that visit.

⁴ Full physical examination at screening (including height); limited physical examination (ear, nose, throat, chest and neck) at subsequent visits.

⁵ Vital signs include heart rate, blood pressure (systolic and diastolic), respiratory rate and oral body temperature. Heart rate and blood pressure to be captured after 5 minutes in supine position. Vital signs must be recorded pre-dose at all visits, and additionally between 3 and 4 hours post-dose on Day 1.

⁶ Pulse oximetry to determine oxygen saturation is to be captured after at least 5 minutes of rest in seated or supine position.

⁷ 12-lead ECG to be measured after at least 5 minutes of rest in supine position.

EVENT	SCREENING	TREATMENT PERIOD ¹				FOLLOW-UP
		D1	D15 (±2D)	D29 (±2D)	ED	
Study days (D)	D-28 till D-1					
Sweat collection	X	X	X	X	X	X
Spirometry ⁸	X	X	X	X	X	X
Clinical safety laboratory tests ⁹	X	X	X	X	X	X
Serology ¹⁰	X					
Pregnancy test ¹¹	X	X		X	X	X
FSH test ¹²	X					
CFTR genotyping		X				
PK blood samples ¹³			X	X	X	
Exploratory biomarkers ¹⁴		X	X	X		
Randomization		X				
Breakfast or snack to be provided ¹⁵		X	X	X		
Study drug dosing						
Study drug dispensing		X	X			
Dispense subject diary	X	X	X	X		
Collect subject diary		X	X	X	X	X
AE assessment						
Concomitant medications						
Optional substudy¹⁶						

⁸ Spirometry must be performed pre-dose at all visits, and additionally between 1 and 2 hours post-dose on Day 1 and Day 29.

CFQ-R = Cystic Fibrosis Questionnaire - Revised; ECG = electrocardiogram; ED = early discontinuation

⁹ Blood and urine samples to be collected for clinical safety laboratory tests.

¹⁰ Serology sample for hepatitis B virus surface antigen, hepatitis C virus antibody and human immunodeficiency type 1 and 2 antibodies.

¹¹ For female subjects of childbearing potential only; serum pregnancy test at screening, urine pregnancy test at other scheduled visits.

¹² For suspected post-menopausal female subjects only (age < 55 years and no menses for ≥ 12 months without a medical cause).

¹³ PK blood samples for GLPG2222 to be taken pre-dose and 0.5, 1, 2, 3, 4, 6 and 8 hours post-dose on Day 15 (or on Day 29 if subject is not available for full PK profiling on Day 15), and pre-dose on Day 29. In case of an early discontinuation visit, one additional sample to be taken pre-dose if study drug is still taken, or at any time during the visit if study drug is no longer taken.

¹⁴ Exploratory biomarkers [REDACTED].

¹⁵ Study drug to be taken once daily in the morning with a breakfast or snack.

¹⁶ Only for subjects who give separate consent to participate in the optional substudy.

AE = adverse event; CFTR = cystic fibrosis transmembrane conductance regulator; FSH = follicle stimulating hormone, PK = pharmacokinetic(s)

EVENT	SCREENING	TREATMENT PERIOD ¹				FOLLOW-UP
		D1	D15 (±2D)	D29 (±2D)	ED	
Study days (D)	D-28 till D-1					
Nasal brushing		X	X	X		

2. ANALYSIS POPULATIONS

The analysis population will always be indicated in a subtitle in the table, listing or figure.

2.1. ALL SCREENED SUBJECTS POPULATION

All subjects who provided informed consent by signing the ICF.

2.2. ALL ENROLLED POPULATION

All subjects who were enrolled into the study, i.e. randomized into the study.

2.3. INTENT TO TREAT POPULATION

All enrolled subjects who received at least one dose of study drug and had at least one post-baseline assessment with efficacy data.

2.4. SAFETY POPULATION

All subjects who received at least one dose of study drug.

2.5. PHARMACOKINETICS POPULATION

Subpopulation of the Safety population, including all subjects who were exposed to GLPG2222 and who have available and evaluable PK data (e.g. excluding all protocol violations/deviations or AEs that may have an impact on the PK analysis).

3. TREATMENT GROUPS

3.1. RANDOMIZED VERSUS ACTUAL TREATMENT

For efficacy parameters, the treatment group as assigned by the randomization will be used in the analysis (i.e., as-randomized analysis).

For safety, the treatment that was actually used by the subject will be applied in the analysis (i.e., as-treated analysis).

Differences between as-treated and as-randomized will be flagged in the listing on subject randomization.

3.2. TREATMENT GROUP LABELS

The following treatment group labels will be used in the tables, listings and figures:

- Pooled placebo
- GLPG2222 50 mg q.d.
- GLPG2222 100 mg q.d.
- GLPG2222 200 mg q.d.
- GLPG2222 400 mg q.d.

3.3. POOLING OF GROUPS

Both placebo groups (from cohort A and from cohort B) will be pooled into one placebo group for the tables/figures but not for the listings. Note that for some tables and some figures, placebo from each cohort can be provided as well.

3.4. SUB-GROUPS

In efficacy part, the following sub-groups analyses will be performed and the following labels will be used in the tables/figures:

- By target C_{trough} at Day 15 (only for GLPG2222 dose levels)
 - Reached target C_{trough} at Day 15 (\geq █ ng/mL)
 - Not reached target C_{trough} at Day 15 ($<$ █ ng/mL)
- By target C_{trough} at Day 29 (only for GLPG2222 dose levels)
 - Reached target C_{trough} at Day 29 (\geq █ ng/mL)
 - Not reached target C_{trough} at Day 29 ($<$ █ ng/mL)
- By target C_{trough} at Day 15 and 29 (only for GLPG2222 dose levels)
 - Reached target C_{trough} at Day 15 and reached target C_{trough} at Day 29
 - Not reached target C_{trough} at Day 15 and not reached target C_{trough} at Day 29
- By sweat chloride (from arm with greatest volume) at baseline
 - Baseline sweat < 40 mmol/L
 - Baseline sweat [40-50[mmol/L*
 - Baseline sweat [50-60[mmol/L*
 - Baseline sweat ≥ 60 mmol/L
- By sweat chloride (mean value from both arms) at baseline
 - Baseline sweat < 40 mmol/L
 - Baseline sweat [40-50[mmol/L*
 - Baseline sweat [50-60[mmol/L*
 - Baseline sweat ≥ 60 mmol/L
- By %FEV1 at baseline
 - Baseline %FEV1 < 40
 - Baseline %FEV1 [40-50[*
 - Baseline %FEV1 [50-70[*
 - Baseline %FEV1 [70-90[*
 - Baseline %FEV1 ≥ 90

*[X1-X2[means $\geq X1$ and $< X2$

These sub-group analyses will be mainly for change from baseline tables, specific tables/figures will be created when needed (Tables and figures will be repeated for each subgroup category). In case no subject has been classified in one of the above category, so the table/figure planned for this category will not be displayed.

3.5. TOTALS OVER GROUPS

A total over all groups will be presented for the general part of the analysis, but not for Safety or Efficacy. Totals will only be shown on tables, but not on listings nor figures.

4. ANALYSIS PERIODS AND ANALYSIS TIME POINTS

4.1. RELATIVE NUMBER OF DAYS

The relative day (DY) is calculated as follows:

- = Visit date – reference date + 1 day, when the visit date is on or after the reference date
- = Visit date – reference date, when the visit date is before the reference date.

The reference date in the study is **Day 1 pre-dose**, which by definition has DY=1. There is no DY=0.

4.2. ANALYSIS PERIODS FOR NON-VISIT DATA

These analysis periods are to be used for allocation of events into periods (e.g., adverse events).

Analysis period	Start period	End Period
Screening	Date of signing the ICF, with 00:00 added as time part.	First treatment administration date(time) - 1 minute
Treatment	First treatment administration date(time)	Study termination date, with 23:59 added as time part in case the time part would be missing or incomplete.

Note that the last analysis period in case of early termination will always be ended by the study termination date (date of last contact, with 23:59 added as time part in case the time part would be missing or incomplete).

4.3. ALGORITHM OF ALLOCATING VISITS TO TIME WINDOWS

All visits (including unscheduled visits but excluding visits without data) will be placed into time windows according to their relative day (DY) in the study, according to the following allocation table:

Visits falling really late in the study will be allocated to a “>Day 29” interval, and will not be shown in tables nor figures, but will only be listed.

Time point label	Target day	Interval lower bound	Interval upper bound
Screening ³	NAP ⁴	NAP ⁴	NAP ⁴
Baseline ¹	NAP ⁴	NAP ⁴	NAP ⁴
Day 1 post-dose ³	NAP ⁴	NAP ⁴	NAP ⁴
Day 15	15	2	21
Day 29	29	22	36
>Day 29 ²	NAP ⁴	37	$+\infty$
Follow-up ³	11-17 days after last visit	NAP ⁴	NAP ⁴

¹ The actual baseline reference value will be determined per parameter as the last available pre-dosing data point, so might differ from this “baseline” visit interval.

² Visits falling really late in the study (relative day > 36; excluding the follow-up visit) will be allocated to a “>Day 29” interval, and will not be shown in tables nor figures, but will only be listed.

³ For the screening, day1 post-dose (vital signs) and follow-up visits, no time window is defined. The visit as recorded in the CRF will be used.

⁴ NAP = Not applicable

For efficacy, PD data, all by-time-point summaries will be based on the visit indicated on the subject’s CRF and will not be placed in time windows.

Tables, figures and listings will present the time points, not the visits.

4.4. SELECTION OF VISITS

It is possible that more than one visit gets allocated into the same time window. In that case, only one visit will be selected for analysis tables and figures. The nonselected visit(s) will only be listed, and flagged as use=no.

The visit with a relative day (DY) closest to the target day will be selected. If there are multiple visits at the same distance of the scheduled visit day (meaning: equal ABS(DY – target day)), then the one latest in time is selected.

In case of multiple screening visits, the last pre-baseline screening measurement (the last visit happening before the scheduled 'Day 1 predose') is selected for analysis. This value (not the original first screening value) was also used in the clinical center to include the subject in the study.

In case more than one parameter is measured per time point (e.g. for lab), the selection is performed per parameter and per time point, not per “sample” and per time point. Missing values are removed before the selection is made.

As baseline reference point, the last nonmissing pre-dosing value will be used. This is normally the scheduled baseline itself. A missing scheduled baseline value will be imputed with the last nonmissing value of a preceding pre-dosing visit. This can be a screening visit or an unscheduled visit prior to the first dose of study medication. If there is an unscheduled measurement taken after the scheduled baseline, before the first dose of study drug, then this unscheduled measurement will be used instead of the scheduled baseline. If there is an

unscheduled measurement at the same datetime as the scheduled baseline, then it is assumed that the unscheduled measurement is taken after the scheduled baseline.

In case the screening visit is used to impute the baseline, the original screening visit as well as the imputed baseline will be presented in the tables. In the listings, only original screening data will be shown: the original screening visit will be shown and flagged as “reference” visit. The imputed baseline will not be shown.

In case an unscheduled visit is used to impute the baseline, the visit will be renamed to “baseline”. The imputed baseline will be presented in the tables. In the listings, the original unscheduled data will be shown and flagged as “reference” visit.

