6.4.3. Vital Signs

Vital signs (i.e. HR, systolic blood pressure [SBP], diastolic blood pressure [DBP], respiratory rate and oral body temperature) will be assessed in a standardized manner at the time points specified in the flow chart. Vital signs must be recorded pre-dose at all visits, and additionally between 3 and 4 hours post-dose on Day 1. HR, SBP and DBP will be measured after 5 minutes in supine position.

Additional collection times, or changes to collection times of blood pressure, HR and body temperature will be permitted, as necessary, to ensure appropriate collection of safety data.

Normal ranges for vital signs parameters are presented in Appendix 2. Any clinically relevant abnormalities should be reported as AEs.

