4.5. HANDLING OF UNSCHEDULED ASSESSMENTS

If there is an unscheduled measurement at the same datetime as a scheduled visit, then it is assumed that the unscheduled measurement is taken after the scheduled visit.

Unscheduled measurements prior to use of the study drug: see section 4.4.

Unscheduled measurements after the first dose of study drug: place into time window (section 4.3) and selection will be made according rules defined in section 4.4.

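### An unscheduled repeat can replace the scheduled Day 15 or Day 29 safety value under SAP 4.3-4.5, which can pull the by-visit safety summaries toward no change

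*SAP*

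**What the plan says.** SAP 4.3 sets the windows, Day 15 covering relative days 2-21 and Day 29 covering 22-36, and fills them without regard to visit type: "All visits (including unscheduled visits but excluding visits without data) will be placed into time windows". SAP 4.5 confirms this for unscheduled measurements after first dose: "place into time window (section 4.3) and selection will be made according rules defined in section 4.4".

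SAP 4.4 then keeps one value per window. "The visit with a relative day (DY) closest to the target day will be selected"; if two are equally distant, "then the one latest in time is selected". The choice is made parameter by parameter ("the selection is performed per parameter and per time point"), so a single repeated test can be swapped on its own. "The nonselected visit(s) will only be listed, and flagged as use=no". For identical date-times, SAP 4.5 adds that "it is assumed that the unscheduled measurement is taken after the scheduled visit".

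The rule has limits. SAP 4.3 takes efficacy and PD summaries from the CRF visit, and does not window screening, Day 1 post-dose or follow-up. The worst-case derivations in SAP 13.2.5, 13.3.5, 13.4.4 and 13.5.4 use all post-baseline values, unscheduled ones included.

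The protocol foresees extra measurements. Section 5.2.7 requires retesting when a liver-test discontinuation criterion is met. Section 6.4.3 states: "Additional collection times, or changes to collection times of blood pressure, HR and body temperature will be permitted, as necessary".

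**The concern.** Repeats are not a random sample of measurements: many are taken because the first value looked wrong. If the repeat then stands in for the first value, an extreme observation is exchanged for one that is, on average, less extreme even when the subject's underlying state has not changed. Values that looked normal are repeated less often, so the exchange leans one way.

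Changes over time in vital signs, SpO2, ECG and laboratory data belong to the primary endpoint (Protocol 4.1). The exposed outputs are:

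- the Day 15 and Day 29 descriptive statistics and changes from baseline;
- the by-time-point entries of the shift and treatment-emergent abnormality tables;
- Table 14.3.2.5 (categorical laboratory shifts), whose description has no worst-case entry.

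With 25 subjects per cohort randomized 2:2:1, each dose group has about 10 subjects and the pooled placebo group about 10, so single values count.

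**Working it through.** The plan states no figure on this point, so there is nothing to reproduce. The check has three parts.

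**1. When a repeat wins.** Inputs: target day T = 15 or 29 (SAP 4.3); visit tolerance ±2 days (flow chart); relative day counted in whole dates (SAP 4.1). A repeat taken k days after a scheduled visit on day s replaces it if |s + k − T| ≤ |s − T|.

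| Scheduled day | Repeat lags that win |
|---|---|
| 13 or 27 | 0-4 days |
| 14 or 28 | 0-2 days |
| 15-17 or 29-31 | 0 only |

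Same-day repeats win on 5 of 5 scheduled days. For later-day repeats, counting each day and lag equally, 5 of 15 combinations win for lags 1-3 and 6 of 35 (17%) for lags 1-7. These are counts of combinations, not forecast frequencies.

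**2. How far one swap moves a value.** Assume first and repeat values are bivariate normal with a stable subject mean, an upper limit at 1.96 SD, and correlation ρ. The documents give no ρ, so 0.5-0.9 is an assumption. The mean of a first value above the limit is φ(1.96)/[1 − Φ(1.96)] = 0.0584/0.0250 = 2.34 SD. The repeat averages ρ × 2.34, and one swap moves the mean of a 10-subject arm by (1 − ρ) × 2.34/10.

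| ρ | Mean of repeat (SD) | Repeat still abnormal | Shift in arm mean (SD) |
|---|---|---|---|
| 0.5 | 1.17 | 19% | 0.12 |
| 0.7 | 1.64 | 33% | 0.07 |
| 0.9 | 2.10 | 59% | 0.02 |

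**3. Upper bound on by-visit abnormality counts.** Suppose every out-of-range value is repeated the same day. The by-visit rate before replacement is P(Z > z), where z is the distance to the limit divided by √(σb² + σw²). Afterwards it is the probability that both values are out of range, with ρ = σb²/(σb² + σw²). The SBP limit (150 mmHg) and SpO2 limit (95%) are from SAP 13.4.3 and 13.5.3. All means and SDs (between/within) are assumptions.

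| Parameter | Assumed | z | ρ | Before | After | Relative loss |
|---|---|---|---|---|---|---|
| SBP > 150 | mean 125, SD 12/8 | 1.73 | 0.69 | 4.2% | 1.5% | 63% |
| SpO2 < 95% | mean 96.5, SD 1.2/1.0 | 0.96 | 0.59 | 16.8% | 7.8% | 54% |
| ALT > ULN | median 0.6 × ULN, log SD 0.4/0.15 | 1.20 | 0.88 | 11.6% | 7.7% | 33% |
| ALT > ULN | median 0.6 × ULN, log SD 0.4/0.25 | 1.08 | 0.72 | 13.9% | 7.3% | 47% |

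If a share f of out-of-range values is repeated, the loss is f times the figure shown, so half-repeated gives half.

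**The case against.** The strongest reply accepts the reading of the rule and disputes its reach. Most of that reply stands.

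- **The abnormal result is not lost.** Worst-case entries appear in the normal-range shift and treatment-emergent tables for laboratory, QT/QTcF, vital signs and SpO2. For QT/QTcF they keep the largest value and the largest change. Abnormality listings are planned, and Protocol 6.4.3-6.4.6 asks for clinically relevant abnormalities to be reported as adverse events. However, the laboratory, vital-sign and SpO2 worst case records only a category, and no worst-case row can correct a mean or a change.
- **The documents contain no policy of repeating every out-of-range value.** Protocol 6.4.6 has such laboratory values flagged and assessed for relevance. The liver retest in 5.2.7 starts from AST/ALT above 3 × ULN with further findings, or above 5 × ULN. Under the ALT assumptions above, z for 3 × ULN is ln(3/0.6)/0.427 = 3.77 or ln(3/0.6)/0.472 = 3.41, so only about 0.01-0.03% of values qualify. The ALT rows therefore do not illustrate that retest. Section 6.4.4 has no repeat provision for SpO2, and 6.4.3 does not name abnormality as the trigger.
- **Same-day laboratory repeats may be uncommon.** SAP 13.2.4 has a central laboratory score the values. A later-day repeat after an on-time or late visit is the one dropped.
- **Displacement can go the other way.** After a normal Day 13 visit, an abnormal unscheduled value on Day 16 would be selected.

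A reader might also infer that dose differences shrink. The documents do not show this: the rule is the same in every arm, and a comparison is distorted only if repeats or abnormal values are more frequent in some arms. Nor can the laboratory mean plots be called biased, because SAP 13.2.7 leaves unscheduled results out of them. That statement does sit awkwardly with SAP 4.4, which selects values for tables and figures alike.

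**Conclusion.** The point holds in a limited form. As written, the SAP lets a same-day repeat, or a repeat 1-4 days after a Day 13/27 visit or 1-2 days after a Day 14/28 visit, replace the scheduled safety value. Where an abnormal result prompted the repeat and the subject's state is stable, the Day 15/29 summaries move toward normal. One swap is worth about 0.02-0.12 SD of a 10-subject arm mean at correlations of 0.9-0.5.

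The overall size cannot be stated, because repeat frequency is not in the documents. The one-third to two-thirds loss of by-visit abnormalities is an illustration of the extreme case, resting on universal same-day repeats and assumed variances. It is not a forecast, and it does not mean that abnormal findings vanish from the safety report.

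Spirometry, although named in the primary safety endpoint, is summarized under SAP section 9 by CRF visit and is unaffected. The change is worth making because it is cheap and concerns the primary endpoint.

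**What to change.** In SAP 4.4 and 4.5, state that the scheduled, CRF-labelled assessment is used for its time point whenever it is non-missing, and that an unscheduled value enters the window only if the scheduled value for that parameter is missing. Leave the worst-case derivations and listings as they are, with all unscheduled values included. This brings displacement to zero in every combination tabulated above. Reconcile SAP 13.2.7 with 4.4 at the same time, saying whether an unscheduled value that fills a gap may appear in the laboratory mean plots.

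The cost is a sentence and a small programming change, with no new data. There is one downside: a repeat taken because the first measurement was technically faulty would be used only if the faulty scheduled result is set to missing, so the SAP should say that such results are to be handled that way before analysis.
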